#### 13.9 **Significance**

Fungal infections continue to be major contributors to morbidity and mortality in children receiving chemotherapy for AML. Although antifungal prophylaxis in these patients will reduce the frequency of IFI, it will not eliminate the risk of these devastating infections. Early diagnosis and therapeutic modifications are paramount to improving patient outcomes. The Platelia *Aspergillus* EIA and the Fungitell Assay are potential diagnostic tools that could improve the time to diagnosis of IFIs. More definitive data regarding the operating characteristics of these 2 biomarkers interpreted simultaneously and separately in the setting of a large pediatric cohort receiving fungal prophylaxis are necessary.

Evaluating the biomarkers first as integrated tests will provide valuable information regarding the utility of each test so that they can be utilized as integral markers in future pediatric cancer trials. Finally, specimens from this study will be stored for potential future investigation. This will allow for the possibility of evaluating future versions of these or other biomarker assays for the identification of IFI in this cohort.

## 14.0 SPECIAL STUDIES SPECIMEN REQUIREMENTS

### 14.1 Single Nucleotide Polymorphisms (This study is optional)

Genotypes of interest in genes mediating immune function will be determined by review of experimental data from AAML0531 and review of the literature. Genotyping will be conducted as part of 1R01 CA133881 and analysis will be performed on the Taqman Open Array Platform according to the manufacturer's instructions.

#### 14.1.1 Sample Collection

##### *Patients Enrolled on AAML1031:*

All samples for ACCL0933 will be obtained from the AML Reference Laboratory from samples submitted on patients enrolled on AAML1031. Thus, no additional sample collection beyond AAML1031 sample collection will occur for patients enrolled on the AAML1031 trial.

##### *All Other Patients:*

For patients not enrolled on AAML1031, 5 mL of peripheral blood should be collected in a purple top tube at the end of Course I, when the patient has an ANC > 1000/ $\mu$ L (and with no circulating blasts).

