#### 1.2.5

To test the association between single nucleotide polymorphisms (SNPs) in genes involved in innate immunity and proven or probable IFI.

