## 2.4 Rationale for Single Nucleotide Polymorphism (SNP) Aim

In addition to early detection of fungal infections, there also is interest in identifying children particularly susceptible to these infections. There is considerable evidence that there is a genetic component to the susceptibility and outcome of infection in both normal and immunocompromised populations. For example, a study using a Danish adoption registry found that premature death from infection is much more heritable compared to premature death from cardiovascular disease or cancer. Redundancy in the immune system may be important for protection against serious infection and in the face of immunosuppression, defects in redundant pathways may be uncovered, leading to invasive bacterial or fungal infections. While defects in immunity may contribute to susceptibility to infection and outcome, excessive inflammation during infection may also contribute to septic shock and mortality. Thus, variation in immunity and inflammatory genes likely plays a role in an individual's susceptibility, response and prognosis related to infection. There is evidence specifically to link SNPs and the risk of fungal infections. For example, Choi and colleagues found that 2 polymorphisms in IL-4 were associated with chronic disseminated candidiasis in patients with acute leukemia. In addition, a polymorphism in *DEFB* was associated with *Candida* carriage in type 1 diabetes. Based on these and other studies, we propose to test for associations between genetic variants in genes mediating innate immunity and IFI.

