### 3.2.2 Diagnosis

Patients must have one of the following diagnoses and/or treatment plans:

- Newly diagnosed *de novo* AML
- First or subsequent relapse of AML
- Secondary AML
- Treatment with institutional standard AML therapy in those without AML (for example myelodysplastic syndrome, bone marrow blasts  $> 5\%$  or biphenotypia).

Please note: Patients with a history of prolonged antifungal therapy (example relapsed AML) are eligible.

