### 9.3.3 Sample size with power justification

A total of approximately 550 eligible patients will be randomized to the 2 arms (at least 275 patients on each arm). Patients will be followed for infection outcome data until criteria in Section 8.3 has been met unless the patient is off study per Section 8.2 prior to meeting criteria in 8.3.

Since the current AAML1031 proposal plans 4 courses of chemotherapy with about 1 month duration for each course, it implies that likely many study participants will be followed for IFI for about 5 months. The power calculation assumes an IFI incidence in the fluconazole group of 8% and an IFI incidence in the caspofungin treatment groups of 2% at 5 months. The hazard ratio is 0.24. We assume up to 10% of patients may have early termination of follow up on IFI due to change in AML therapy such as refractory disease, relapse, or death. It is estimated that up to 25% of patients treated on or per AAML1031 may go to SCT prior to finishing all 4 courses. Therefore, altogether up to 35% patients may not be followed until the end of 5 months for IFI. With at least 275 patients on each arm, a planned 5-month follow up on each patient and up to 35% patients being censored by 5 months, we have about 80% power to detect the expected difference in time-to-IFI curves between the 2 arms (8% vs. 2% at 5 months) in a log rank test with 2-sided alpha level of 0.05. In the calculation, both failure and censoring are assumed to follow an exponential distribution during the 5 months. The majority of the censoring events prior to 5 months are expected to be due to SCT which likely occur later in the 5 months, so the exponential censoring distribution might not be a very good approximation but should be conservative in power consideration.

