### Host factorsa

- Recent history of neutropenia ( $< 0.5 \times 10^9$  neutrophils/L [ $< 500$  neutrophils/mm^3] for  $> 10$  days) temporally related to the onset of fungal disease
- Receipt of an allogeneic stem cell transplant
- Prolonged use of corticosteroids (excluding among patients with allergic bronchopulmonary aspergillosis) at a mean minimum dose of 0.3 mg/kg/day of prednisone equivalent for  $> 3$  weeks
- Treatment with other recognized T cell immunosuppressants, such as cyclosporine, TNF- $\alpha$  blockers, specific monoclonal antibodies (such as alemtuzumab), or nucleoside analogues during the past 90 days
- Inherited severe immunodeficiency (such as chronic granulomatous disease or severe combined immunodeficiency)

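### SNP DNA is taken from blood without recording prior allogeneic transplant, so some genotypes analysed as the patient's own may be the donor's (minor)

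*Combined protocol and SAP*

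**What the plan says.** Objective 1.2.5 is "To test the association between single nucleotide polymorphisms (SNPs) in genes involved in innate immunity and proven or probable IFI", and objective 1.2.6 builds prediction models from SNPs and clinical covariates. Section 2.4 bases both on host genetics: it cites a "genetic component to the susceptibility and outcome of infection in both normal and immunocompromised populations" and argues that gene variation "plays a role in an individual's susceptibility, response and prognosis related to infection".

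The DNA source depends on AAML1031 enrolment (Section 14.1.1):

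- **Enrolled on AAML1031:** "All samples for ACCL0933 will be obtained from the AML Reference Laboratory from samples submitted on patients enrolled on AAML1031". No specimen type, time point or blast status is given.
- **All other patients:** "5 mL of peripheral blood should be collected in a purple top tube at the end of Course I", with an ANC above 1000/μL and no circulating blasts. Section 7.2.2 and the footnote to the Section 7.1 table present those two conditions as optimal rather than required. No non-blood or stored pre-transplant sample is offered as an alternative.

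Section 3.2.2 lists "First or subsequent relapse of AML" among the eligible diagnoses. The exclusions in Sections 3.2.4 to 3.2.8 cover certain diagnoses, recent or treated IFI, drug hypersensitivity, and pregnancy and lactation. Prior transplant is not among them.

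The SNP part of Section 9.3.4 provides for false discovery rate control, analyses with and without ethnicity adjustment, and possible stratification by treatment arm. It does not mention transplant history or donor chimerism.

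**The concern.** A patient who relapsed after an allogeneic transplant, and who was never enrolled on AAML1031, can enter the trial and give blood for genotyping after count recovery. Waiting for neutrophil recovery and absence of blasts guards against leukaemic DNA. It does not guard against donor DNA, because the recovering cells may be the donor's. The call may then be the donor's genotype or a mixture, and a mixture can look like a heterozygote that neither person is.

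The plan neither prevents this nor records what would be needed to detect it at analysis. At stake are the SNP-IFI tests and the SNP terms of the prediction model, which rest on few events. Section 13.8.1 expects 18 + 4 = 22 IFI among 440 participants in the antigen study. The Section 9.3.3 assumptions give about the same number for all 550 patients once early censoring is counted. With so few events, one or two attributed to the wrong genotype matter.

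**Working it through.** **No stated figure to reproduce.** The documents give no power, effect size, allele frequency or participation rate for the SNP aim, and no share of patients with a prior transplant. The event count can be derived.

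**Events.** Inputs from Section 9.3.3: IFI of 8% and 2% at 5 months, 275 per arm, up to 35% censored by 5 months, exponential times.

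- Hazards per month: −ln(0.92)/5 = 0.01668 and −ln(0.98)/5 = 0.00404. Their ratio is 0.242, against the stated 0.24.
- Without censoring: 275 × 0.08 + 275 × 0.02 = 27.5 events.
- With censoring hazard −ln(0.65)/5: 17.9 + 4.5 = 22.4 events.

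About 22 is thus an upper figure for the SNP aim under these assumptions, because it needs every patient to be genotyped and SNP sampling is optional.

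**How often a donor's call differs (assumed minor allele frequency 0.3, Hardy-Weinberg).**

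- Unrelated donor: 1 − (0.49² + 0.42² + 0.09²) = 0.575.
- Full sibling, sharing 0, 1 or 2 alleles by descent with probability 1/4, 1/2, 1/4: 0.25 × 0.575 + 0.5 × 0.42 + 0.25 × 0 = 0.354.

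**Calculation 1: affected patients at average IFI risk.** Assumptions: 550 patients, overall IFI 5% (the mean of 8% and 2%, no censoring), carrier frequency 20% or 40%, two-sided unadjusted alpha 0.05. A fraction m of samples is replaced by an unrelated donor's genotype. With p1 and p0 the true risks in carriers and non-carriers, the observed risks are P = (1 − m)p + 0.05m.

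Example: for a true odds ratio of 3 and 20% carriers, p1 = 0.1028 and p0 = 0.0368. At m = 10%, P1 = 0.0975 and P0 = 0.0381, an odds ratio of 2.73.

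| Affected samples m | True OR 2 seen as | True OR 3 seen as | Power for OR 3 |
|---|---|---|---|
| 0 | 2.00 | 3.00 | 75–78% |
| 1% | 1.99 | 2.97 | 74–77% |
| 5% | 1.93–1.94 | 2.83–2.86 | 72–74% |
| 10% | 1.87–1.88 | 2.67–2.73 | 68–70% |
| 20% | 1.74–1.77 | 2.39–2.48 | 60% |

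If half the donors share the patient's carrier status, the loss is about half.

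**Calculation 2: affected patients at higher IFI risk.** If a fraction f of genotyped patients is affected and they have k times the IFI hazard, their share of events is s = fk/(1 − f + fk). The observed log hazard ratio is about (1 − s) ln 3. With 22 events and 51% carriers (1 − 0.49), power is Φ[(1 − s) × ln 3 × √(22 × 0.51 × 0.49) − 1.96].

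| f | k | Share of events s | HR 3 seen as | Power |
|---|---|---|---|---|
| 0 | – | 0 | 3.0 | 73% |
| 2% | 1 | 2% | 2.9 | 71% |
| 5% | 1 | 5% | 2.8 | 69% |
| 5% | 3 | 13.6% | 2.6 | 60% |
| 10% | 1 | 10% | 2.7 | 64% |
| 10% | 3 | 25% | 2.3 | 49% |

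The share of events governs the loss. A 5% share of patients is harmless at equal risk, but at three times the hazard it puts about 14% of events in question. The last row needs 10% prevalence, a tripled hazard and unrelated donors all at once. The two calculations start from different event counts (27.5 and 22), so their power figures are not interchangeable. Both are nominal; false discovery rate control would lower them.

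**The case against.** **The donor's genotype may be the relevant one.** The aim concerns immune genes, and after an allogeneic transplant the blood-derived immune cells are the donor's. For genes expressed in leukocytes the donor's call may be functionally right; for genes acting in other tissues it is less so. This stands. It rules out saying that associations are necessarily diluted, and it argues against compulsory exclusion. It does not rescue the plan, which never says which genotype is intended and cannot tell these patients apart. A mixed sample represents neither person.

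**The affected share may be tiny.** This also stands: the documents give no figure. A reader might take one from Section 9.3.3, which says "It is estimated that up to 25% of patients treated on or per AAML1031 may go to SCT prior to finishing all 4 courses". That estimate concerns transplant after entry. The SNP sample is due at the end of Course 1, and Section 8.3 ends IFI observation when conditioning begins. Likewise, allogeneic transplant in the Appendix II host factors is part of a general diagnostic list and does not describe this population. Neither shows how many patients enter with a prior transplant.

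**AAML1031 samples.** A reader might infer that DNA from these patients is blast-rich. The documents support only that no blast condition is stated here. Section 14.1.1 relies on samples collected under another protocol, which is not available and may specify remission specimens. The Section 7.1 footnote gives the end-of-Course-1, optimally blast-free timing without an AAML1031 exception, although Section 7.2.2 applies the extra draw only to other patients. Blasts are the patient's own cells and change a call only where the leukaemia is altered at that locus. No size can be given for this part.

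**Not every relapsed patient is affected.** Someone enrolled on AAML1031 at diagnosis who later relapses may have an earlier sample at the reference laboratory.

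**Conclusion.** The gap is real on the text: relapsed patients with a prior allogeneic transplant can enter, blood is the only DNA source outside AAML1031, and neither collection nor analysis takes account of transplant history. SNP-IFI associations and the SNP terms of the prediction model may be distorted. The direction is not certain, because the donor's genotype may be relevant for some genes and transplant history may itself be related to IFI risk.

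The size rests on assumptions about prevalence, hazard, donor relationship, allele frequency and effect. At equal risk the loss is small with 5% or fewer affected samples and material nearer 10 to 20%; a raised hazard moves that threshold down. The fall in power from 73% to 49% is an extreme corner and should not be read as the expected effect.

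Severity is minor. The aim is optional and secondary, and no randomized comparison of the two arms is affected. The missing specimen description for AAML1031 patients is a smaller documentation point.

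**What to change.** 1. In Section 14.1.1, require a flag for prior allogeneic transplant, taken from the baseline history that Section 7.1 already requires.
2. In Section 9.3.4, pre-specify that the SNP-IFI tests and the SNP terms of the prediction model are repeated without flagged patients, or with a banked pre-transplant sample where one exists, and that both sets of results are reported.
3. In Section 14.1.1, state the specimen type and remission status of the reference-laboratory samples used for AAML1031 patients. Reconcile the sampling condition for other patients, which 14.1.1 states as a requirement and 7.1 and 7.2.2 as a preference.

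The cost is some protocol wording and one data field, with no extra blood draw. The repeat analysis loses a few patients and possibly one or two events; the analysis of all genotyped patients remains alongside it.

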#### 14.1.2 Labeling:

Label the tubes with the patient's COG ID number, protocol ID number, BPC #, date and time of collection.

**APPENDIX II: EORTC/MSG CRITERIA**

**Criteria for proven invasive fungal disease except for endemic mycoses**

Analysis and specimen	Molds a	Yeasts a
Microscopic analysis: sterile material	Histopathologic, cytopathologic, or direct microscopic examination b of a specimen obtained by needle aspiration or biopsy in which hyphae or melanized yeast-like forms are seen accompanied by evidence of associated tissue damage	Histopathologic, cytopathologic, or direct microscopic examination b of a specimen obtained by needle aspiration or biopsy from a normally sterile site (other than mucous membranes) showing yeast cells—for example, Cryptococcus species indicated by encapsulated budding yeasts or Candida species showing pseudohyphae or true hyphae c
Culture		
Sterile material	Recovery of a mold or “black yeast” by culture of a specimen obtained by a sterile procedure from a normally sterile and clinically or radiologically abnormal site consistent with an infectious disease process, excluding bronchoalveolar lavage fluid, a cranial sinus cavity specimen, and urine	Recovery of a yeast by culture of a sample obtained by a sterile procedure (including a freshly placed [!24 h ago] drain) from a normally sterile site showing a clinical or radiological abnormality consistent with an infectious disease process
Blood	Blood culture that yields a mold d (e.g., Fusarium species) in the context of a compatible infectious disease process	Blood culture that yields yeast (e.g., Cryptococcus or Candida species) or yeast-like fungi (e.g., Trichosporon species)
Serological analysis: CSF	Not applicable	Cryptococcal antigen in CSF indicates disseminated cryptococcosis

a If culture is available, append the identification at the genus or species level from the culture results.

b Tissue and cells submitted for histopathologic or cytopathologic studies should be stained by Grocott-Gomori methenamine silver stain or by periodic acid Schiff stain, to facilitate inspection of fungal structures. Whenever possible, wet mounts of specimens from foci related to invasive fungal disease should be stained with a fluorescent dye (e.g., calcofluor or blankophor).

c *Candida*, *Trichosporon*, and yeast-like *Geotrichum* species and *Blastoschizomyces capitatus* may also form pseudohyphae or true hyphae.

d Recovery of *Aspergillus* species from blood cultures invariably represents contamination

## Criteria for probable invasive fungal disease except for endemic mycoses

---

### Host factorsa

- Recent history of neutropenia ( $< 0.5 \times 10^9$  neutrophils/L [ $< 500$  neutrophils/mm^3] for  $> 10$  days) temporally related to the onset of fungal disease
- Receipt of an allogeneic stem cell transplant
- Prolonged use of corticosteroids (excluding among patients with allergic bronchopulmonary aspergillosis) at a mean minimum dose of 0.3 mg/kg/day of prednisone equivalent for  $> 3$  weeks
- Treatment with other recognized T cell immunosuppressants, such as cyclosporine, TNF- $\alpha$  blockers, specific monoclonal antibodies (such as alemtuzumab), or nucleoside analogues during the past 90 days
- Inherited severe immunodeficiency (such as chronic granulomatous disease or severe combined immunodeficiency)

### Clinical criteriab

#### Lower respiratory tract fungal diseasec

- The presence of 1 of the following 3 signs on CT:
  - Dense, well-circumscribed lesions(s) with or without a halo sign
  - Air-crescent sign
  - Cavity

#### Tracheobronchitis

- Tracheobronchial ulceration, nodule, pseudomembrane, plaque, or eschar seen on bronchoscopic analysis

#### Sinonasal infection

- Imaging showing sinusitis plus at least 1 of the following 3 signs:
  - Acute localized pain (including pain radiating to the eye)
  - Nasal ulcer with black eschar
  - Extension from the paranasal sinus across bony barriers, including into the orbit

### CNS infection

- 1 of the following 2 signs:
  - Focal lesions on imaging
  - Meningeal enhancement on MRI or CT

### Disseminated candidiasisd

- At least 1 of the following 2 entities after an episode of candidemia within the previous 2 weeks:
  - Small, target-like abscesses (bull's-eye lesions) in liver or spleen
  - Progressive retinal exudates on ophthalmologic examination

### Mycological criteria

#### Direct test (cytology, direct microscopy, or culture)

- Mold in sputum, bronchoalveolar lavage fluid, bronchial brush, or sinus aspirate samples, indicated by 1 of the following:
  - Presence of fungal elements indicating a mold
  - Recovery by culture of a mold (e.g., *Aspergillus*, *Fusarium*, *Zygomycetes*, or *Scedosporium* species)

#### Indirect tests (detection of antigen or cell-wall constituents)e

- Aspergillosis
  - Galactomannan antigen detected in plasma, serum, bronchoalveolar lavage fluid, or CSF
- Invasive fungal disease other than cryptococcosis and zygomycoses
  - $\beta$ -D-glucan detected in serum

---

**NOTE.** Probable IFD requires the presence of a host factor, a clinical criterion, and a mycological criterion. Cases that meet the criteria for a host factor and a clinical criterion but for which mycological criteria are absent are considered possible IFD.

a Host factors are not synonymous with risk factors and are characteristics by which individuals predisposed to invasive fungal diseases can be recognized. They are intended primarily to apply to patients given treatment for malignant disease and to recipients of allogeneic hematopoietic stem cell and solid-organ transplants. These host factors are also applicable to patients who receive corticosteroids and other T cell suppressants as well as to patients with primary immunodeficiencies.

b Must be consistent with the mycological findings, if any, and must be temporally related to current episode.

c Every reasonable attempt should be made to exclude an alternative etiology.

d The presence of signs and symptoms consistent with sepsis syndrome indicates acute disseminated disease, whereas their absence denotes chronic disseminated disease.

e These tests are primarily applicable to aspergillosis and candidiasis and are not useful in diagnosing infections due to *Cryptococcus* species or *Zygomycetes* (e.g., *Rhizopus*, *Mucor*, or *Absidia* species). Detection of nucleic acid is not included, because there are as yet no validated or standardized methods.

